Study Protocol and Statistical Analysis Plan

EFFECTIVENESS OF COMBINED AEROBIC AND STRENGTH TRAINING IN ACUTE AND CHRONIC ADAPTATIONS IN PATIENTS WITH HEART FAILURE

Date: 19/10/2017

PROTOCOL

Title

Effectiveness of combined aerobic and strength training in acute and chronic adaptations in patients with heart failure

Participants

Patients with chronic heart failure (CHF) that underwent to a hospital-based cardiac rehabilitation (CR) program in the Lisbon district Hospitals will be recruited. The study will be performed in the Cardiovascular Rehabilitation Center of the University of Lisbon (CRECUL) at the Lisbon University Stadium (EUL). The participants will be randomized into one of the following exercise groups: A) combined exercise training with more aerobic training and less strength training (CAT); B) combined exercise training with more strength training and less aerobic training (CST); Inclusion criteria: CHF patients; receiving optimal medical therapy for CHF (including an angiotensin-converting enzyme inhibitor or an angiotensin receptor blocker and a beta-blocker unless a contraindication is evident) with a stable condition for more than 1 month (no hospitalization for heart failure (HF), no change in medication, and no change in New York Heart Association (NYHA) functional class. Exclusion criteria: if they are younger than 18 years or are unable to sign informed consent; unstable angina pectoris; and orthopedic or neurological limitations to exercise. Patients will be stratified (by age and etiology) and randomized consecutively to CAT or CST in the beginning of the exercise at community. There will be 2 assessment moments (M): M0) before starting the exercise training (ExT) program (baseline) and M1) 3 month after starting the ExT.

Sample size was calculated (G-Power, Version3.1.3) assuming a difference in carotid intima-media thickness (IMT) between groups of 5% to be a clinical important difference with a SD of 0.16, $\alpha=0.05$, $1-\beta=0.95$ and an expected dropout rate of 26%. The calculations yielded a total minimum sample size of 28 participants (14 in each group).

Recruitment

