ExT is a major component of rehabilitation/secondary prevention interventions, inducing significant beneficial changes in mechanisms of pathophysiology, exercise tolerance, functional capacity and QoL, while a positive impact on hospitalization and mortality reduction. There has been growing interest in the characteristics and modalities of exercise training able to induce optimal benefits. High intensity and interval mode have been shown to induce greater benefits than moderate intensity and continuous mode regimes. Considering the current body of evidence of high-intensity interval training (HIIT) in CHF, HIIT demonstrated to be more efficient, result in long term adherence, which be an important practical aspect to consider during the ExT and consequently optimized improvements in central and peripheral adaptations [25]. More studies are needed to proof their safety and benefits on this type of patients.

Additionally, there has been sound rationale for the inclusion of ST to the HIIT, which has been also shown able to yield benefits in terms of exercise capacity and QoL. It is well known that combined AT and ST is the preferred exercise intervention to reverse or attenuate the loss of MM and improve exercise and functional capacity, muscle strength in this individuals [19]. But there are underlying mechanisms from the ST in the CHF patient's peripheral capacity that remains unidentified. And isn't known what is the benefits of combine different proportions of AT and ST.

For that reason, the investigators will test two proportions in combined training, CAT and CST. There haven't been any data on the so called combined regimes, which include both aerobic exercise with HIIT and ST and the investigators will evaluate the effects of acute and chronic response.

PURPOSE

The research project will contribute to a better understanding in several aspects that are unexplained by scientific research. The purpose of this research project are:

- 1) To determine the effectiveness of a ExT programme with different proportions of CAT and CST in promoting cumulative effects in acute and chronic adaptations in CHF patients;
- 2) To identify the mechanisms of the potential improvement in effectiveness promoted by ST;

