13. STATISTICAL ANALYSIS

Data will be analyzed in M0 and M1. It will be tested the data for normality and homogeneity of variance with the Shapiro Wilk and Levene's tests, respectively. Data analysis will be described according to the established purposes for this project (descriptive values: mean, standard deviation, range, % change) and comparisons of means will be used for all purposed

outcomes intra and inter groups. Baseline characteristics between groups will be evaluated with oneway ANOVA. Mixed between within subjects ANOVA will be conducted in a 2 (pre vs post ExT) design to assess efficiency of the program. When a significant interaction is observed, t tests, or Wilcoxon signed-rank tests will be used to determine where the interaction occurred.

M0 versus M1 will be compared to evaluate the changes in patients and trace the necessary timespan for such changes using General Linear Mixed Model Analysis for repeated measures with Tukey's posthoc procedure for the mean comparisons. Pearson product moment correlation coefficient or Spearman's rank correlation coefficient will be used to study the relationship between different variables by group and correlation coefficients will be compared between groups. Statistical significance will be set at an alpha level of 0.05. Other statistical procedures can be done.

Statistical analyses will be conducted using Statistical Package for the Social Sciences (SPSS) 22.0 (IBM SPSS Statistics, Chicago, IL, USA).

Data analysis will allow peer reviews publication, slide presentations and oral communications in national and international conferences, during year of 2018 and beginning of 2019 to present all the results of the project.

REFERENCES

1. R. Belardinelli, D. Georgiou, G. Cianci and A. Purcaro, *10-year exercise training in chronic heart failure: A randomized controlled trial*, J Am Coll Cardiol **60** (2012), no. 16, 1521-1528.
2. G. Loncar, S. Fülster, S. von Haehling and V. Popovic, *Metabolism and the heart: An overview of muscle, fat, and bone metabolism in heart failure*, Int J Cardiol **162** (2013), no. 2, 77-85.
3. J. Y. Tabet, P. Meurin, A. B. Driss, H. Weber, N. Renaud, A. Grosdemouge, F. Beauvais and A. Cohen-Solal, *Benefits of exercise training in chronic heart failure*, Arch Cardiovasc Dis **102** (2009), no. 10, 721-730.

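### No outcome is designated primary, and all proposed outcomes (about 56 by a reader's count) are tested at 0.05 with nothing limiting error across them

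*Combined protocol and SAP*

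**What the plan says.** Purpose 1 (PURPOSE) is to determine the effectiveness of two mixes of aerobic and strength training "in promoting cumulative effects in acute and chronic adaptations in CHF patients". It names no outcome. The list of assessments under STUDY DESIGN and the measures in sections 1 to 10 carry no ranking.

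cIMT stands out in one place only. The sample size, under Participants, is calculated "assuming a difference in carotid intima-media thickness (IMT) between groups of 5% to be a clinical important difference with a SD of 0.16".

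Section 13 does not mention cIMT. It states that "comparisons of means will be used for all purposed" "outcomes intra and inter groups" (one sentence, broken across lines). Two models follow, each with its own role:

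- "Mixed between within subjects ANOVA will be conducted in a 2 (pre vs post ExT) design to assess efficiency of the program". If the interaction is significant, t or Wilcoxon tests follow.
- "General Linear Mixed Model Analysis for repeated measures with" Tukey's procedure, to evaluate change from M0 to M1 and how long it takes.

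Correlations are estimated by group and compared between groups. The section then sets one threshold and leaves the list of methods open: "Statistical significance will be set at an alpha level of 0.05. Other statistical procedures can be done".

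**The concern.** Purpose 1 is an effectiveness comparison, and the sample size is stated in confirmatory terms (alpha 0.05, power 0.95). A plan of that kind should say in advance which result answers the question. Here dozens of outcomes face the same threshold, with no hierarchy, gatekeeping or adjustment between them. The two safeguards in section 13 do not help: the interaction gate is itself run at 0.05 for each outcome, and Tukey's procedure covers mean comparisons within one outcome's model.

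At stake is what the trial can claim. Even if the two mixes were equivalent on everything measured, a few outcomes would be expected to cross 0.05. Nothing in the plan prevents one of them from being presented as the evidence for purpose 1 while cIMT shows no difference.

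**Working it through.** **The plan's own figure.** The only design figure is the total of 28 (14 per group). Reading 5% as 0.05 absolute with SD 0.16, a two-sided two-sample comparison needs n per arm = 2 × (1.960 + 1.645)² × 0.16² / 0.05² ≈ 266.1, so 267, or 268 with the t distribution. This does not reproduce 14. A repeated-measures interaction comes near 28 only under a high pre-post correlation that the document does not give. That is a separate matter; here the figure matters only because it shows which outcome was used for sizing.

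**Counting outcomes (sections 1 to 10).** Section 13 gives no list, so this is a reader's count.

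| Domain | Count | What is counted |
|---|---|---|
| Echocardiogram | 8 | LVEF, 2 volumes, 2 diameters, transmitral flow, tissue Doppler, mitral regurgitation |
| CPET | 8 | maximal HR, HR recovery at 1 and 3 min, peak VO2, exchange ratio, ventilatory threshold, 2 ventilatory equivalents |
| Arterial stiffness | 5 | PWV to 3 sites, beta index, augmentation index |
| Carotid ultrasound and blood pressure | 6 | diameter, distensibility, cIMT, alpha index, systolic, diastolic |
| DXA | 3 | bone, lean, fat |
| Accelerometry | 3 | sedentary, light, moderate to vigorous |
| Functional tests | 5 | five tests |
| Handgrip | 2 | two hands |
| 1RM | 6 | six machines |
| SF-36 | 10 | 8 subscales, 2 summaries |

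Sum: 8 + 8 + 5 + 6 + 3 + 3 + 5 + 2 + 6 + 10 = 56. PWV and the beta index, listed in two sections, are counted once. Merging related measures and leaving out accelerometry brings the count to 47; splitting further and adding derived measures brings it to 68 or 69. Within-arm tests and correlation comparisons are not counted.

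**Expected false between-arm differences** = 0.05 × number of true nulls, whatever the correlation.

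- 56 nulls: 0.05 × 56 = 2.8
- 50 nulls (for example, if the six 1RM outcomes truly differ): 0.05 × 50 = 2.5
- 47 and 69 nulls: 2.35 and 3.45

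**Chance of at least one.** Under independence it is 1 − 0.95^k, so 1 − 0.95^56 = 0.943. With equal correlation r it comes from integrating over a shared normal component. The values of r are assumptions.

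| Nulls | r = 0 | r = 0.3 | r = 0.5 | r = 0.7 |
|---|---|---|---|---|
| 47 | 0.91 | 0.79 | 0.61 | 0.40 |
| 50 | 0.92 | 0.81 | 0.62 | 0.40 |
| 56 | 0.94 | 0.83 | 0.65 | 0.42 |
| 69 | 0.97 | 0.88 | 0.70 | 0.45 |

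Equal correlation is a simplification. A simulation with the ten domains above as clusters and 10 completers per arm (28 × 0.74 = 20.7) gave about 0.88 with correlation 0.5 within and 0.1 between domains, and about 0.74 with 0.7 and 0.3.

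**The case against.** The sample size paragraph publicly commits the trial to cIMT and calls a 5% difference clinically important, so cIMT could be called primary in all but name. This stands in part. A reader holding the document can see that a claim built on, say, the back scratch test does not rest on the sizing outcome. It would therefore be too strong to infer that chance results could not be told from planned ones. But an implied primary outcome binds nobody, and section 13 treats cIMT like every other measure.

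A reader might also infer that section 13 leaves open which of its two models decides, or that it lets significance in either one carry the claim. The text does not support that. The mixed ANOVA is assigned to the program's efficiency, and the mixed model to change and its timing. With two arms, two times and complete data the two interaction tests also coincide; they can part only through patients without M1. Nor does the plan contain a rule that any significant outcome counts as success. It contains no success rule at all, and that is the gap.

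The magnitudes are open to challenge too. The count depends on splitting, the outcomes are not equally correlated, and the arms differ by design (in months 2 and 3, 1 versus 3 sets and 10 versus 5 intervals, section 11), so the number of true nulls is unknown. All of this stands. The probabilities are illustrations; only 0.05 times the number of nulls is free of a correlation assumption.

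**Conclusion.** The point holds. This document designates no primary outcome, cIMT is implied only by the sample size, and section 13 tests all proposed outcomes at 0.05 with no control across them. About 2.8 false between-arm differences are expected if all 56 outcomes are null, and 2.5 if 50 are. At assumed equal correlations of up to 0.7, the chance of at least one among 56 is between 0.42 and 0.94, far above 0.05.

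The count is a reader's, and the correlations are assumed because the documents give none. The qualitative conclusion depends on neither: with only 10 null outcomes at correlation 0.5 the chance is still 0.29. The finding is limited to this document; a registry record, not available here, might name a primary outcome. It should be corrected before analysis, and a wording change is enough.

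**What to change.** Add to section 13, before analysis:

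- The single confirmatory test is the group-by-time interaction (CAT versus CST, M0 to M1) for cIMT measured at rest before the session, as placed under STUDY DESIGN, at two-sided alpha 0.05, from the planned analysis of program efficiency.
- If resting cIMT is recorded at more than one rest time, state which is used, or use their mean. (The 15- and 30-minute rest in section 4 is stated for blood pressure.)
- State how patients without M1 are handled. With "an expected dropout rate of 26" per cent this matters, because a standard repeated-measures ANOVA omits them. One option is to estimate the same interaction in the mixed model already planned, which includes all randomised patients with any data.
- All other outcomes, acute post-session measures, within-arm tests and correlation comparisons are exploratory, reported with estimates and 95% confidence intervals. Other procedures are labelled post hoc.

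cIMT is the default because the trial is sized on it. Another single outcome, fixed before analysis, would also serve.

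**Cost.** No new data are needed. Fewer results can be called significant, and the acute part of purpose 1 has no confirmatory test. Power for cIMT is likely low. Reading 5% as 0.05 absolute, with SD 0.16 and 10 completers per arm, the SD of change is 0.16 × √(2(1 − r)). That is 0.160 at an assumed pre-post correlation of 0.5 (power about 0.10) and 0.072 at 0.9 (power about 0.32). A non-significant cIMT result must therefore be reported with its confidence interval and not as evidence of no difference.
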